On the other hand, osteophytes formation at the entheseal regions of the joints in PsA is distinctive feature compared with RA (13). The formation of osteophytes is tightly regulated by anabolic pathways, which resembles the pathogenesis of new bone formation in ankylosing spondylitis (AS). Tumor necrosis factor (TNF) inhibition was unable to halt the structural progression in AS patients (14-16), it also lacked efficacy in stopping the progression of osteophytes in PsA patients (17). Inhibition of IL-17 by secukinumab was effective in the treatment of both AS (18) and PsA (12). Secukinumab also decreased the rate of radiographic joint damage regarding to erosion and joint space narrowing (12). However, it is unknown if it has any effect in the progression of osteophytes. In an animal model, although over-expression of IL-17 alone failed to induce entheseal and periosteal bone formation, inhibition of IL-17 leaded to significant reduction of such bone formation in an IL-23 overexpression model (19). Moreover, IL-17A accelerates bone formation by stimulating the proliferation and osteoblastic differentiation of mesenchymal progenitor cells after injury (20). It is worth exploring if secukinumab could prevent the progression of osteophytes in PsA patients.

Aims and hypotheses to be tested:

Hypothesis

IL-17 inhibition by secukinumab could lead to healing of existing erosion, and prevent progression of osteophytes, and resolution of dactylitis in PsA patients.

Aims

The aim of this randomized, double-blind, placebo-controlled study is to evaluate the protective effects of secukinumab on the healing of joint erosion and prevention of progression of osteophytes in PsA patients using HR-pQCT and US.

Objectives

Primary outcome

Difference in changes in the volume of erosions on metacarpophalangeal joints (MCP) 2-4 measured by HR-pQCT at 24 and 48 weeks between secukinumab and placebo group.

Secondary outcomes

- The percentage of erosions with healing determined using HR-pQCT on MCP 2-4 at 24 and 48 weeks including 1). A decrease in erosion volume of ≥0.4 mm³ from baseline, and 2). The presence of grade 2 osteosclerosis at the margin of erosion.
- 2) Changes in volume and width of erosion using HR-pQCT at 24 and 48 weeks;
- 3) Changes in the height of osteophytes using HR-pQCT at 24 and 48 weeks;
- Marginal osteosclerosis (semi-quantitative and quantitative) using HR-pQCT at 24 and 48 weeks;

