- 5) Changes in joint space volume using HR-pQCT at 24 and 48 weeks

Exploratory outcomes

- 1) Changes in US-parameters in dactylitis, enthesitis and synovitis at 24 and 48 weeks
- 2) Changes in van der Heijde-Sharp score on radiograph at 24 and 48 weeks.
- 3) Changes in patients-reported-outcomes (SF-36, Psoriatic Arthritis Impact of Disease (PsAID)) and functional disability (HAQ) at 24 and 48 weeks
- 4) Changes in biomarkers (Pro-C2, C-Col10, COMP, MCP-1, Dkk1 and sclerostin) at 24 and 48 weeks

Plan of Investigation:

Subjects 120 biologic DMARDs naïve PsA patients attending the outpatient clinic of the Prince of Wales Hospital (PWH), North District Hospital (NDH), Tai Po Hospital (TPH), Queen Elizabeth Hospital (QEH) and Tseung Kwan O Hospital (TKOH) who fulfilled the Classification Criteria for Psoriatic Arthritis (CASPAR), will be recruited. The main inclusion criteria are: 1) ≥18 years old; 2) without severe deformity in MCP joints (MCPJ) which would influence the longitudinal assessment of HR-pQCT; 3) with active disease, which is defined as three or more tender joints and three or more swollen joints, despite previous treatment with nonsteroidal anti-inflammatory drugs, disease-modifying antirheumatic drugs. These 120 patients will be screened for the presence of erosion at the head of MCPJ 2-4 using HRpQCT. The first 40 patients with erosion will be randomised in a 1:1 ratio to secukinumab (n=20) or placebo (n=20) group. Based on a study using high-resolution CT in 41 PsA patients, 41% of the patients had at least one erosion, and 90% of the erosions were in MCPs (5). The resolution of the highresolution CT is 0.4 mm, which is almost 5 folds lower than HR-pQCT (82 µm). Therefore, we estimated that over 1/3 of the PsA patients will have at least one erosion in MCPs. Thus, screening 120 patients using HR-pQCT should be adequate to recruit 40 patients with erosions on MCPJ 2-4.

All study procedures will be performed in PWH after recruitment from non-PWH site.

Randomisation will be performed using a computer-generated randomisation list provided by the hospital pharmacist, using a permuted blocks design with block sizes of 4 and 6. Allocation concealment will be ensured by the use of sequentially numbered, opaque, sealed envelopes. Treatment will be masked to patients and investigators.

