All possible side effect of the biologic and synthetic DMARDs used the study will be explained to the participants by the research nurse and the treating physician. To monitor the possible side effect, complete blood count, liver function tests and renal function tests will be performed every visit. Chest X-rays will be obtained at baseline and at the end of the study. The treating physician records all nonserious and serious adverse events, all reports of drug exposure during pregnancy, and all reports of misuse and abuse of the Novartis drug, other medication errors and uses outside of what is foreseen in the protocol, if necessary, make treatment adjustments in accordance with the protocol. Serious adverse events are defined as any adverse reaction resulting in any of the following outcomes: a lifethreatening condition or death, a significant or permanent disability, a medically significant event, hospitalization or prolongation of hospitalization, a congenital abnormality, or a birth defect. All adverse events from this trial will be reported to local IRB and Health Authority by the investigator according per requirement as holder of certificate of clinical trial. Any SAEs, reports of drug exposure during pregnancy and reports of Study Drug misuse or abuse, including initial and follow up reports, arising from the Study in subjects exposed to the Study Drug, as soon as it becomes available, but in any event within fifteen (15) calendar days of becoming aware of such information, will be forwarded to Novartis by transmitting it to Novartis Patient Safety team.

Erosion assessment by HR-pQCT

Image acquisition

Metacarpal bone erosion will be assessed at MCP 2-4 of the more severely affected or the dominant hand if both hands are equally affected using a HR-pQCT system (XtremeCT II; Scanco Medical AG, Bruttisellen, Switzerland). This system enables the simultaneous acquisition of CT slices with an isotropic resolution (voxel size) of 82 μ m. HR-pQCT scanning will be performed by a single investigator who is blinded to all the clinical information of the patients. A single examination will be performed for

measurements of MCP 2-4. An anteroposterior scout view will be used to define the region of interest (ROI). The scan region will be 80 slices distal and 242 slices proximal of the upper margin of the head of MCP3. Scan time will be around 8 min per patient and scan (8). The scans will be performed at baseline, 24 and 48 weeks.

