This is the first study assessing erosion healing using HR-pQCT. Erosion healing is evidenced by a decrease in erosion volume and the presence of bone apposition at the margin of the erosion. Based on our preliminary data, the smallest detectable change of erosion volume, which was calculated on

the basis of 29 individual erosions as suggested by Bruynesteyn et al. (25), was 0.4 mm³. Meanwhile, a grade 2 osteosclerosis means dramatic bone apposition at the erosion margin (>75%). Therefore, a decrease in erosion volume of \geq 0.4 mm³ from baseline, and the presence of grade 2 osteosclerosis at the surface of erosion at 24 or 48 weeks is considered as strong evidence of erosion healing.

Osteophytes

The maximal height of each osteophyte will be documented by assessing the maximal distance between the surface of the osteophyte and the original cortical bone surface using the open source DICOM viewer Osirix V3.2 (Rosslyn, VA, USA) (17). The change of the maximal height between baseline and 52 weeks will be calculated.

Images will be evaluated by two independent readers blinded to the clinical data. Based on the posthoc analysis of a 6-months open-label randomized-controlled trial conducted by us (26), intra-observer reproducibility was 0.987, 0.994, 0.982, and 0.983 for erosion width, depth, volume and quantitative osteosclerosis, respectively. Inter-observer reproducibility as determined by intraclass correlation coefficient was: 0.977, 0.979, 0.962, and 0.974 for erosion width, depth, volume and quantitative osteosclerosis, respectively. Inter-reader agreement for the assessment of detecting the presence or the grade of osteosclerosis was also high (Kappa: 0.81~0.91).

Joint Space Width analysis

Volumetric joint space will be quantified using an algorithm developed by consensus from the Study grouP for eXtreme Computed Tomography in Rheumatoid Arthritis (SPECTRA) [33]. The 3-D JSW including mean (JSW.Mean, mm), maximum (JSW.Max, mm), minimum (JSW.Min, mm), SD (JSW.SD, mm), asymmetry [defined as JSW.Asymm = ratio of JSW.Max/JSW.Min,] as well as volume (JSV, mm³) will be calculated. Cuts through the sagittal and coronal planes (2-dimensional) will be automatically generated for visualization. A rheumatologist with HR-pQCT expertise will review all joints and score for degree of luxation (none, subluxation, luxation) and bone-on-bone contact (yes, no).

Ultrasound assessment of synovitis, dactylitis, enthesitis and digital pulleys

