Data processing and analysis Statistical analyses will be performed using the Statistics Package for Social Sciences (SPSS). Data will be analysed in an intention-to-treat manner. Patients who discontinued treatment or violated treatment protocol will be excluded from analysis. Missing data are assumed missing at random and will be treated using a multiple Imputation method (30). Based on the pilot study and our previous experience, the missing data is estimated to be less than 5%. Descriptive statistics will be used for demographic and clinical variables included frequencies, means and standard deviations, median and interquartile range. T-test, Mann-Whitney U test and Chi-square test will be used to evaluate differences in baseline characteristics between secukinumab group and placebo group. Changes of the outcome measurements between groups will be tested using t-test, Mann-Whitney U test, repeated measures analysis of variance (ANOVA) or Chi-square test where appropriate. Multivariate linear or logistic regression will be used to explore the association between the use of secukinumab and outcome measurements adjusting for baseline characteristics. A 2-tailed probability value of p < 0.05 is considered statistically significant.

Reference

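### Erosion-volume change is compared without baseline volume as a covariate: the planned test is valid, but naming that covariate in the primary model would usually gain some precision at 20 per arm

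*Combined protocol and SAP*

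**What the plan says.** All places are in the combined protocol and SAP.

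- **Objectives, primary outcome:** "Difference in changes in the volume of erosions on metacarpophalangeal joints (MCP) 2-4 measured by HR-pQCT at 24 and 48 weeks", compared between secukinumab and placebo.
- **Data processing and analysis, main comparison:** "Changes of the outcome measurements between groups will be tested using t-test, Mann-Whitney U test, repeated measures analysis of variance (ANOVA) or Chi-square test", whichever is appropriate. No covariate is attached to any of these tests.
- **Same section, adjusted analysis:** "Multivariate linear or logistic regression will be used to explore the association between the use of secukinumab and outcome measurements adjusting for baseline characteristics". The covariates are not listed and the stated purpose is exploratory.
- **Plan of Investigation, Subjects:** "The first 40 patients with erosion will be randomised in a 1:1 ratio to secukinumab (n=20) or placebo (n=20) group". The list is made "using a permuted blocks design with block sizes of 4 and 6", and no stratification factor is stated.
- **Erosion assessment by HR-pQCT, Image acquisition:** "The scans will be performed at baseline, 24 and 48 weeks". Baseline volume will therefore be available for every randomised patient who is scanned as planned.

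**The concern.** The change score subtracts the whole of the baseline value. That is the best use of baseline only if follow-up volume rises one for one with baseline volume. If the slope is below 1, patients with larger erosions at entry tend to show more decrease (or less increase) for reasons unrelated to treatment. The change-score difference then contains (1 − slope) times whatever baseline difference arose by chance, with opposite sign.

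Nothing in the design limits that difference, because simple permuted blocks balance numbers and not erosion volume. With 40 patients, two things are at stake: precision, which is scarce, and the status of the adjusted result. If the adjusted and unadjusted results differ, the adjusted one is exploratory and its covariates were never fixed.

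Repeated measures ANOVA does not close the gap. With baseline as one of the time levels it tests group by time, and it does not condition on baseline volume.

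**Working it through.** **The plan's own figure.** The documents give no effect size, SD or power, so there is no power calculation to reproduce. The 40 patients come from screening yield: 120 × 1/3 = 40.

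**Inputs.** From the documents: 20 per arm, two-sided 5%. Assumed: one volume per patient, roughly normal volumes, equal SDs at baseline and follow-up, and a baseline to follow-up correlation ρ of 0.5, 0.7 or 0.9. With equal SDs the slope equals ρ.

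**1. Chance imbalance.** The SD of the difference in baseline means is √(2/20) = 0.316 baseline SDs. An imbalance above 0.5 SD lies beyond 0.5/0.316 = 1.58 standard errors, so its two-sided probability is 0.114.

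**2. Carry-over.** Given imbalance b, the change-score difference is shifted by −(1 − ρ)b. For b = 0.5 SD the size is 0.25, 0.15 and 0.05 baseline SDs at ρ = 0.5, 0.7 and 0.9.

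**3. Precision.** Var(ANCOVA)/Var(change) = (1 + ρ)/2 × f, where f = 1 + 1/(40 − 4) = 1.0278 is the cost of estimating the slope. Power uses the noncentral t distribution (38 against 37 df), with the effect set so that the change t-test has 80%.

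**4. Type I error by imbalance.** Under the null and given b, the change difference is normal with mean −(1 − ρ)b and variance 0.1(1 − ρ²). The pooled variance is 2(1 − ρ) × χ²₃₈/38. Integrating over |b| > 0.5 gives the fourth column. The last column follows because the overall rate is 5%: (5.0 − 0.114 × column 4)/0.886.

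| ρ (assumed) | Variance ratio | ANCOVA power | Type I error of change t-test, imbalance > 0.5 SD | Type I error otherwise |
|---|---|---|---|---|
| 0.5 | 0.75 × 1.0278 = 0.771 | 89% | 13.6% | 3.9% |
| 0.7 | 0.85 × 1.0278 = 0.874 | 85% | 10.2% | 4.3% |
| 0.9 | 0.95 × 1.0278 = 0.976 | 81% | 6.7% | 4.8% |

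A separate check of the last column gave 4.1%, 4.4% and 4.6%, within about 0.2 percentage points. ANCOVA stays at about 5% in both sets of trials.

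**5. Limits.** Break-even is ρ = 2/1.0278 − 1 = 0.946. As ρ approaches 1 the ratio approaches 1.028, so the largest loss is 2.8%.

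**6. What the documents say about ρ.** They report reader agreement only: "Inter-observer reproducibility as determined by intraclass correlation coefficient was: 0.977, 0.979, 0.962, and 0.974 for erosion width, depth, volume and quantitative osteosclerosis". The volume figure is 0.962, and the intra-observer figure is 0.982. If reading errors at the two scans are independent and reliability is similar here, these are rough ceilings on ρ. The ratio there is 1.008 to 1.019, a loss of 0.8% to 1.9%.

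**7. Sensitivity.** For ρ from 0.3 to 0.98, the ratio is 0.60 to 0.83 if the follow-up SD is 0.9 of the baseline SD, and 0.73 to 1.03 if it is 1.1 times. For lognormal volumes analysed in mm³ the ratio is about 0.7 with a log-SD of 1. With a log-SD of 0.5 it is 0.83, 0.92 and 0.94 at log-scale ρ of 0.7, 0.9 and 0.95.

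**The case against.** The strongest reply is that nothing planned is wrong. A test of change answers the stated primary question, is unbiased over randomisation and holds its level. This stands. The high conditional error rates apply to about 11% of randomisations and are offset by rates below 5% in the other 89%. A reader who saw only the 13.6% might infer that the primary test is anti-conservative, and it is not. With strongly skewed volumes (lognormal, log-SD 1), even the conditional error of the t-test falls to 4.4% and 3.6% at log-scale ρ of 0.9 and 0.95.

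A second reply is that adjustment is already planned, and baseline volume would be a natural member of the covariate set. So it would be too strong to say that the plan has no adjusted analysis. What remains is narrower: the covariate is unnamed and the model is not primary. The plan also tests baseline differences between arms, but does not link those tests to the choice of covariates.

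A third reply is that erosions may be so stable over 24 to 48 weeks that adjustment gains nothing. The documents cannot exclude this. Reader agreement is not the correlation between scans months apart, but a value above 0.946 is possible. This limits the claim about size. It does not remove the recommendation, because the loss in that case is small.

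**Conclusion.** The point stands as a recommended improvement in efficiency, not as a defect in validity. The direction is well supported: adjusting for baseline volume usually helps and costs little on the mm³ scale. The size is not established. Under the normal, equal-SD model the variance falls by 23%, 13% or 2% at ρ of 0.5, 0.7 or 0.9. There is no gain at 0.946 and a loss of at most about 3% above it.

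A reader might infer that the trial gives up substantial power. The documents do not support that, because they give no correlation, slope, SD or degree of skew. The larger gains need a moderate correlation, a follow-up SD that differs from the baseline SD, or marked skew, and all of these are assumptions.

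**What to change.** In Data processing and analysis, name as the primary analysis of erosion volume an ANCOVA at each of weeks 24 and 48, with baseline erosion volume as a prespecified covariate. A mixed model with arm-by-visit and baseline-by-visit terms is an alternative. With complete data and unstructured covariance it gives the same estimates at each week. The baseline-by-visit term matters: with assumed correlations with baseline of 0.9 (week 24) and 0.7 (week 48), and 0.85 between the weeks, the common slope is 0.923. Then 0.923 − 0.7 = 0.22 of the imbalance still reaches week 48, against 1 − 0.7 = 0.30 unadjusted. Keep the unadjusted t-test or Mann-Whitney U test as sensitivity analyses.

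**Cost:** wording, one degree of freedom per week, and at most about 3% of variance on the mm³ scale. No new data are needed.

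A log or rank scale is optional. The plan allows for skewed data ("means and standard deviations, median and interquartile range"), but any such scale should be fixed before unblinding, and the 3% limit does not cover it. In simulations where change did not depend on baseline size, rank or log ANCOVA had roughly 63% to 71% power against 79% for the t-test. That scenario is itself strained, since its additive model makes about 23% to 44% of follow-up volumes negative.

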The patients will be randomly assigned to the secukinumab group or placebo group. Patients will be followed-up at weeks 2, 4 and then every 12 weeks until week 52. Patients will receive subcutaneous placebo or secukinumab 150 mg once a week from baseline for 4 weeks, and then once every 4 weeks from week 4 onwards. The study flow is shown in Figure 1. Changes in the baseline treatment, e.g. the dosage of conventional synthetic DMARDs (csDMARDs) including methotrexate, leflunomide, hydroxychloroquine, or sulfasalazine or the addition of a new csDMARD (individually or in combination), as well as changes in the dosage or the addition of steroids or nonsteroidal antiinflammatory drugs were allowed after week 12 if the patient cannot achieve minimal disease activity (MDA) (Table 1) (see appendix 1 for the treatment protocol). For patients who fulfil the criteria for biologic DMARDs (bDMARDs) (Appendix 2) and are willing to be started on bDMARDs, the code will be broken, and they can either pay out of pocket or can apply for the Samaritan Fund for financial assistance, provided they must household-based pass а financial assessment (http://www.ha.org.hk/visitor/ha visitor index.asp?Content ID=10048&Lang=ENG&Dimension=100). Patients who have started bDMARDs apart from secukinumab will be excluded from the efficacy assessment. Adverse effects will be recorded.

Evaluation of disease activity and severity

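### The exploratory adjusted model takes undefined "use" of secukinumab as its treatment term, so a placebo patient who starts open-label secukinumab could be analysed as treated rather than as randomised

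*Combined protocol and SAP*

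**What the plan says.** The statements that bear on this point are in three places of the combined protocol and SAP.

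- **Data processing and analysis, adjusted model:** "Multivariate linear or logistic regression will be used to explore the association between the use of secukinumab and outcome measurements adjusting for baseline characteristics". No other covariate-adjusted analysis is named, and use is not defined.
- **Data processing and analysis, analysis population:** "Data will be analysed in an intention-to-treat manner", followed at once by "Patients who discontinued treatment or violated treatment protocol will be excluded from analysis".
- **Data processing and analysis, main tests:** "Changes of the outcome measurements between groups will be tested using t-test, Mann-Whitney U test, repeated measures analysis of variance (ANOVA) or Chi-square test". These are unadjusted and worded by group.
- **Treatment:** for patients who meet the bDMARD criteria and "are willing to be started on bDMARDs, the code will be broken". They then fund the drug themselves or apply to a means-tested fund. The section adds: "Patients who have started bDMARDs apart from secukinumab will be excluded from the efficacy assessment".
- **Objectives and Plan of Investigation:** the primary outcome is a change "measured by HR-pQCT at 24 and 48 weeks between secukinumab and placebo group", and the first 40 patients with erosion are "randomised in a 1:1 ratio to secukinumab (n=20) or placebo (n=20) group".

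**The concern.** In a placebo-controlled trial without crossover, use and assignment are the same variable and the wording would not matter. Here they can come apart. The Treatment section removes starters of other biologics but not starters of secukinumab, so a placebo patient who starts open-label secukinumab remains in the efficacy assessment. Taken literally, that patient has used secukinumab.

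Whether a patient switches is decided after randomisation and depends partly on how that patient is doing. If switchers are coded as users, placebo patients with poorer courses join the secukinumab side, and the comparator becomes the placebo patients who did not switch. Baseline adjustment corrects only the part of that selection that baseline values predict. The adjusted estimate could then disagree with the between-group tests in the same paragraph for reasons unrelated to the drug. With 20 patients per arm, a few switchers are enough to move it.

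**Working it through.** **No plan figure to reproduce.** The documents give no switching rate, effect size, SD or power on which this point depends. Only the 20 per arm and the two-sided 0.05 level come from the plan. Everything else below is assumed. Positive values mean a worse outcome on the secukinumab side.

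**Step 1. Readings of the text for a placebo patient who starts open-label secukinumab.**

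| Reading | Support in the text | Coding in the model |
|---|---|---|
| As randomised | Intention-to-treat sentence | Placebo |
| As treated | Wording of the regression sentence; Treatment section keeps the patient in | User |
| Excluded | Sentence dropping discontinuers and violators | Not in the model |

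No sentence chooses among them.

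**Step 2. Bias under no drug effect, simple model.** Let k of 20 placebo patients switch. Switch-prone patients are equally common in both arms, and their outcome is worse by d SD.

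- By randomised group, with everyone kept: bias 0.
- By use: the 20 + k users have mean (20 × (k/20) × d + k × d)/(20 + k) and the non-users have mean 0, so the bias is 2kd/(20 + k).
- Switchers excluded: bias kd/20.

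| k | d | By use | Excluded | Type I error, by use (simulated) |
|---|---|---|---|---|
| 2 | 0.5 | 0.09 | 0.05 | 0.056 |
| 2 | 1.0 | 0.18 | 0.10 | 0.074 |
| 4 | 0.5 | 0.17 | 0.10 | 0.066 |
| 4 | 1.0 | 0.33 | 0.20 | 0.139 |
| 6 | 0.5 | 0.23 | 0.15 | 0.092 |
| 6 | 1.0 | 0.46 | 0.30 | 0.229 |

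Example, k = 4 and d = 1: 2 × 4 × 1/24 = 0.33. Over 4,000 simulated trials per setting, with one baseline covariate unrelated to outcome, coding by randomised group gave bias near 0 and type I error of 0.050 to 0.058.

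**Step 3. Bias when switching follows a prognostic score.** Let the score correlate r with outcome, and let the k switchers average m SD on it. The bias by use is r × m × [k/(20 + k) + k/(20 − k)]. For k = 4 the bracket is 4/24 + 4/16 = 0.417.

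- The worst 4 of 20 switch (m = 1.33 for a normal score): 0.3 × 1.33 × 0.417 = 0.17 and 0.5 × 1.33 × 0.417 = 0.28.
- Any 4 of the worst 8 switch (m = 0.93): 0.12 and 0.19 for r = 0.3 and 0.5.
- The worst 4 switch and the model adjusts for a baseline covariate that captures half of the prognostic variance: about 0.09 and 0.14 (simulated). At three quarters, the bias is at most about 0.05 and 0.08.

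**Step 4. With a true effect.** Assume a benefit of 0.90 SD and that switchers obtain half of it, 0.45. By randomised group the estimate is 0.90 − 4 × 0.45/20 = 0.81. By use, with the worst 4 switching and no baseline capture, the mean benefit among users is (20 × 0.90 + 4 × 0.45)/24 = 0.825. Subtracting the bias from Step 3 gives 0.825 − 0.17 = 0.66 for r = 0.3 and 0.825 − 0.28 = 0.55 for r = 0.5.

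**The case against.** The best defence is that use is simply a loose name for the treatment arm. The trial has two arms, the paragraph declares intention to treat, and the neighbouring sentences speak of groups. That may be what was meant. It cannot be relied on, because the sentence after the intention-to-treat statement contradicts it, and because the authors used group wording for the other tests but not here. The cautious reading therefore stands: the coding is undefined. A reader might infer that the plan deliberately replaces randomised group with treatment received, but no sentence says so.

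A second defence is that switchers would be dropped as discontinuers or violators. This is possible, although the Treatment section implies that they stay, and a start on a bDMARD that the protocol permits is not clearly a violation. Exclusion would not restore the comparison either, as the table in Step 2 shows.

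Three further objections stand. The regression is exploratory, and neither the primary outcome nor the main tests are worded by use. Switching also depends on willingness and funding, so the non-users are not only placebo patients who did well; this makes a strict worst-4 rule close to a worst case. Finally, nothing in the documents ties the bDMARD criteria to change in erosion volume, so the strength and even the direction of the bias are conditional.

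**Conclusion.** The point holds as an undefined model term with a plausible harmful reading. If placebo patients who start open-label secukinumab are coded as users, the only adjusted estimate becomes an as-treated comparison. With 4 of 20 switching and no drug effect, the bias against secukinumab is roughly 0.1 to 0.3 SD. This rests on an assumed number of switchers, on switchers having a worse prognosis, and on baseline capturing at most about half of it. With fuller capture the bias falls below 0.1 SD.

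A reader might go on to infer that the primary comparison is compromised by this wording, or that a bias against secukinumab is certain. The documents support neither: the primary outcome is stated by group, and the bias depends on coding and switching behaviour that the plan does not describe. The matter deserves correction because this is the only adjusted analysis and the remedy is slight.

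**What to change.** In Data processing and analysis:

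1. Make the explanatory term of the linear and logistic models *randomised group (secukinumab or placebo), whatever treatment was later received*.
2. State that these models are fitted to all randomised patients. Reconcile with the intention-to-treat statement both the exclusion of discontinuers and violators in this section and the exclusion of starters of other bDMARDs in the Treatment section. Changing the term alone removes the as-treated bias, but the randomised comparison is fully restored only if these exclusions are also kept out of the model.
3. Label any analysis by actual exposure as non-randomised and supplementary.

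The cost is a few sentences of text and no new measurements. Scheduled week 24 and 48 scans should be used for patients who change treatment; the multiple imputation already planned can cover missing values. The resulting estimate includes any dilution from switching, such as 0.81 rather than 0.90 SD in Step 4, and should be described that way. If the authors already meant assigned arm, the change only makes that explicit.
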